5.2.5. Other Analyses

Other pharmacokinetic analyses may be performed as deemed appropriate.

5.3. SAFETY ANALYSES

5.3.1. Adverse Events

Adverse events will be mapped to a Medical Dictionary for Regulatory Activities (MedDRA) version 26.1 preferred term and system organ classification. If a subject experiences multiple events that map to a single preferred term during the same treatment phase, the greatest severity grade and strongest investigator assessment of relation to study medication will be assigned to the preferred term for the appropriate summaries. Should an event have a missing severity or relationship, it will be classified as having the highest severity and/or strongest relationship to study medication.

The occurrence of TEAEs will be summarized by treatment group using preferred terms (PT), system organ classifications (SOC), severity, and/or relationship. A similar summary of (Serious) TEAEs related to study drug will be generated. Separate summaries of treatment-emergent SAE, events of special interest, events leading to the discontinuation of roluperidone, and events leading to death will be generated by SOC and PT. Additionally, an overall summary of the number of subjects experiencing each of these types of TEAEs, along with the overall number of events of each type will be presented. All adverse events reported will be listed for individual subjects showing both verbatim and preferred terms. All adverse events that occurred prior to the initiation of study treatment will be excluded from the tables but will be included in the listings. Any treatment-emergent adverse events occurring after the EOS visit will not be summarized.

The overall summary table will include following types:

- Any TEAE
- Any serious TEAE

Final Version

- Any drug related TEAE
- Any drug related serious TEAE
- Any AESI TEAE
- TEAEs by maximum severity
- TEAEs by maximum relationship
- Any TEAE leading to drug discontinuation
- Any TEAE leading to death

Missing onset dates will be imputed as previously outlined in Section 3.2.3.1 as required to determine treatment-emergent events.

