3. OVERVIEW OF STUDY DESIGN

3.1. Study Design

This is a prospective, open-label, one-sequence, inpatient, clinical study of CYP2D6 normal metabolizer (NM) subjects with moderate to severe negative symptoms of schizophrenia. be coadministered to subjects already being administered roluperidone to determine its effect on the PD and PK of roluperidone. Eligible subjects will undergo 3 study phases as follows:

- Screening Phase: Between 2 and up to 28 days during which study eligibility will be established and subjects receiving psychotropics will be washed out. Discontinuation of psychotropics must occur at least 2 days prior to the start of Treatment Period 1 (Day 1). Subjects will be admitted to the site on Day -2 and complete a Baseline Visit on Day -1.
- **Treatment Phase 1**: After the Baseline Visit (Day -1), roluperidone 64 mg/day will be administered as a monotherapy for 7 days (Days 1-7).
- Treatment Phase 2: Concomitant administration of olanzapine 10 mg/day and roluperidone 64 mg/day for 10 days, starting on Day 8 (Days 8-17). Subjects may be discharged from the clinic at least 48 hours after the last administration of the study drugs and after the collection of the last plasma sample; however, the inpatient period may be extended at the discretion of the investigator.

An End of Study (EOS) visit will take place at least 14 days after the last dose of study treatment. After the EOS visit, the medications and clinical care of the subject will be managed

Figure 1: Study Design Diagram

as per the judgement of the investigator/clinician.

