6.1.6. End of Study/Early Termination

All subjects will return to the site for subsequent EOS assessments 14 (+2) days after receiving their last dose in Treatment Phase 2.

If a subject is terminated early from the study, a PK sample and a blood sample for chemistry and hematology will be drawn as soon as possible together with any relevant safety assessments.

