7. SUBJECT COMPLETION/WITHDRAWAL

7.1. Completion

A subject will be considered to have completed the study if he or she completed all required assessments at Day 19. Subjects who prematurely discontinue for any reason before completion of Day 19 will not be considered to have completed the study.

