9.2. Procedures

9.2.1. All Adverse Events

All adverse events, whether serious or non-serious, will be reported from the time a signed and dated informed consent form is obtained until completion of the last study-related procedure (may include contact for follow-up of safety). Serious adverse events, including those spontaneously reported to the investigator within 30 days after the last dose of study drug, must be reported using the Serious Adverse Event Form. The sponsor will evaluate any safety information that is spontaneously reported by an investigator beyond the time frame specified in the protocol.

All events that meet the definition of a serious adverse event will be reported as serious adverse events, regardless of whether they are protocol-specific assessments.

All adverse events, regardless of seriousness, severity, or presumed relationship to study therapy, must be recorded using medical terminology in the source document and the CRF. Whenever possible, diagnoses should be given when signs and symptoms are due to a common etiology (eg, cough, runny nose, sneezing, sore throat, and head congestion should be reported as "upper respiratory infection"). Investigators must record in the CRF their opinion concerning the relationship of the adverse event to study therapy. All measures required for adverse event management must be recorded in the source document and reported according to sponsor instructions.

The sponsor assumes responsibility for appropriate reporting of adverse events to the regulatory authorities. The sponsor will also report to the investigator all serious adverse events that are SUSARs. The investigator (or sponsor where required) must report these events to the appropriate Institutional Review Board (IRB) that approved the protocol unless otherwise required and documented by the IRB.

Subjects must be provided with a "study card" indicating the name of the investigational study drug, the study number, the investigator's name, a 24-hour emergency contact number, and, if applicable, excluded concomitant medications.

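### The SAP's end-of-study cut-off keeps reportable late SAEs and deaths out of the summary tables, and the cut-off date for early terminators is unclear

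*SAP*

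**What the plan says.** **Tabulation.** SAP 5.3.1: "Any treatment-emergent adverse events occurring after the EOS visit will not be summarized". The sentence covers all treatment-emergent events. The SAP's definition of a treatment-emergent event (3.2.5) has a start, the first dose of study drug, but no end.

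**Listing.** The same SAP section states: "All adverse events reported will be listed for individual subjects showing both verbatim and preferred terms". Section 9 of the SAP plans Listings 16.2.7.1 (adverse events) and 16.2.7.2 (serious adverse events).

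**Reporting.** Under protocol 9.2.1, all adverse events are reported from consent until the last study-related procedure, which may include a safety follow-up contact. Serious events go on the Serious Adverse Event Form, "including those spontaneously reported to the investigator within 30 days after the last dose of study drug".

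**Timing of the EOS visit.** Protocol 3.1 says: "An End of Study (EOS) visit will take place at least 14 days after the last dose of study treatment". SAP 1.1 and the synopsis methodology agree, and the synopsis duration section gives 14 days with a 2-day allowance after the last dose. Protocol 6.1.6 instead places the visit "14 (+2) days after receiving their last dose in Treatment Phase 2". It then asks for samples and relevant safety assessments as soon as possible from subjects terminated early. The schedules in both documents put EOS and early termination (ET) in one column, at Day 31 (+2).

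**The concern.** The reporting window for serious events and the tabulation window end on different days, and the SAP does not acknowledge the difference. An event can be treatment-emergent by the SAP's definition and reportable as serious under the protocol, yet be removed from every summary table. Safety and tolerability of coadministration are the primary objective (SAP section 2), and the SAE, AESI and death tables are where a reader looks for that answer. With about 18 subjects, one event more or less visibly changes a table.

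The cut-off also depends on a visit whose date is not clearly defined for a subject who stops early, so the programmer would have to decide what counts as the EOS visit.

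**Working it through.** **Inputs.**
- Last planned dose: Day 17 (protocol 3.1, SAP 1.1).
- EOS visit: 14 (+2) days after the last dose (protocol 6.1.6, synopsis).
- SAE reporting limit: 30 days after the last dose (protocol 9.2.1).
- Tabulation limit: the EOS visit (SAP 5.3.1).
- Planned enrolment about 18, with at least 12 to complete (protocol 8.1, SAP 3.1).

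**Step 1: reproduce the scheduled visit day.** 17 + 14 = Day 31 and 17 + 16 = Day 33. This matches the schedule entry of Day 31 (+2).

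**Step 2: end of the SAE reporting window.** 17 + 30 = Day 47.

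**Step 3: days that are reportable but not tabulated, for a completer.**
- EOS on Day 31: 47 − 31 = 16 days; 16/30 = 53%.
- EOS on Day 33: 47 − 33 = 14 days; 14/30 = 47%.

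The SAP rule turns on when the event occurs and the protocol limit on when it is reported. The gap therefore concerns events that start after EOS and are reported by Day 47. An event that starts before EOS and is reported later is unaffected.

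**Step 4: tables affected.** Tables 14.3.1.1 (overall summary), 14.3.1.6 (serious), 14.3.1.7 (serious and related), 14.3.1.8 (special interest, where serious) and 14.3.1.10 (leading to death).

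**Step 5: weight of a single event.** One subject is 1/18 = 5.6% of the planned safety set, or 1/12 = 8.3% if only the minimum of 12 receive the combination. This is the weight of one event if it occurs. The documents give no rate from which to predict how many would.

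**Step 6: early terminators, passages side by side.**
- The synopsis, protocol 3.1 and SAP 1.1 count from the last dose of study treatment, so every dosed subject has an EOS date.
- Protocol 6.1.6 says that all subjects return, but counts from the last Treatment Phase 2 dose. A subject who stops in Phase 1 has no such dose.
- The same section's as-soon-as-possible contact for early termination is neither called the EOS visit nor said to replace it or precede it.
- The schedule merges EOS and ET. The SAP takes the final day on study from the EOS eCRF page (3.2.5) and equates study completion with the EOS visit date (3.2.3.1), with no rule for early termination.

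The passages favour a later EOS visit for these subjects but do not settle which contact sets the cut-off.

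**The case against.** **The events are not lost.** This stands. All reported adverse events are listed, and in a study of this size a late death or SAE would be read from the listing and the narrative. The defect is that the tables would not agree with the listings. The SAP says explicitly that pre-treatment events leave the tables but stay in the listings; it gives no such explanation for events after EOS. A reader might infer that late events are dropped altogether, and the documents do not support that.

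**The 30-day window is passive.** This also stands. It covers serious events spontaneously reported to the investigator, and no contact is scheduled after EOS. The 14 to 16 days are therefore not a period of active collection, and a table extended to Day 47 would rest on incomplete ascertainment. That calls for a footnote. It does not justify leaving out an event that was reported.

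**For non-serious events the cut-off is reasonable.** This stands. Their reporting ends with the last study-related procedure, so an EOS cut-off broadly matches collection. It applies equally to non-serious AESIs such as T-wave changes, which should not be tabulated to 30 days.

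**Early terminators do have an EOS date.** This stands in part. Most passages date EOS from the last dose of study treatment, and only 6.1.6 is narrower. The inconsistency remains, and the SAP cut-off depends on resolving it.

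**Conclusion.** The concern holds for serious events and deaths. For each completer, 14 to 16 of the 30 post-dose days (47% to 53%) lie outside the tables, assuming dosing to Day 17 and an EOS visit within its 14 (+2) day window. A later EOS visit, which the at-least-14-days wording would permit, would shorten the gap.

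A reader might go further and infer that subjects stopped for safety get the shortest safety window. If an ET contact 0 to 2 days after the last dose (assumed timing) were taken as the EOS visit, 30 − 2 = 28 to 30 − 0 = 30 of the 30 days would fall outside the tables. The documents allow that reading but do not state it. If EOS takes place 14 (+2) days after the last dose, the gap is the same 14 to 16 days as for completers. Even on the strict reading, the event that prompted withdrawal starts before the ET contact and is summarised, the 30-day SAE provision still runs from the last dose, and unresolved SAEs are followed (protocol 9.2.2). Nor does the allowance of 18 − 12 = 6 non-completers count high-risk subjects: protocol 7.3 lists non-safety reasons for leaving as well.

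A reader might also infer that a missed EOS visit would go unnoticed, because a completer is someone who "completed all required assessments at Day 19" (protocol 7.1). The EOS visit includes a triplicate ECG, and SAP section 6 names missing ECGs as identifiable deviations, so that does not follow.

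What remains is a mismatch between reporting and tabulation that should be corrected before database lock, and an ambiguous cut-off date for early terminators.

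**What to change.** **SAP 5.3.1.** Include SAEs (among them serious AESIs) and deaths with onset up to 30 days after the last dose of either study drug in Tables 14.3.1.1, 14.3.1.6 to 14.3.1.8 and 14.3.1.10. Keep the EOS cut-off for non-serious events. Footnote those tables to say that reporting after EOS is spontaneous only. State that all post-EOS events remain in Listings 16.2.7.1 and 16.2.7.2.

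**Protocol 6.1.6 and the schedules.** Reconcile the Phase 2 wording, the as-soon-as-possible early-termination assessments and the shared EOS/ET column with the synopsis, protocol 3.1 and SAP 1.1. The SAP should then name the date that serves as the EOS cut-off for a subject who terminates early.

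**Cost.** Minor programming and a wording clarification. The SAE change uses reports that the protocol already requires. The downsides are that late events come from passive reporting, so their absence after EOS is weak evidence, and that serious events will have a longer tabulation window than non-serious ones. The footnote should say both.

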5.3.2. Clinical Laboratory Assessments

All laboratory parameters collected at each center's local laboratory will be standardized by converting values in original units to values in standard units and classified as normal, low, or high based on normal ranges supplied by the local laboratories and upon employing standardization.

Laboratory evaluations (including hematology, biochemistry, and urinalysis) will be listed by Treatment Phase and time point. Descriptive summaries of selected (quantitative) clinical laboratory results, and changes from Study Baseline (for Treatment Phase 1) and from Treatment Phase 2 Baseline (for Treatment Phase 2), will be presented by time point and treatment group.

The number and percentage of subjects experiencing treatment-emergent clinically significant laboratory abnormalities will be summarized by treatment group. See Table 2 for parameter specific criteria. All abnormalities that occur post-baseline, regardless of Baseline status will be included. Additionally, shifts in laboratory values with reference to the normal range from Baseline to 48 hours post-dose and from Baseline to EOS will be summarized by treatment.

Listings will be provided for subjects with any laboratory results outside the reference ranges, as well as for subjects with any potentially clinically significant (PCS) laboratory results as defined in Table 2.

Table 2. Criteria For Potentially Clinically Significant Laboratory Tests

Laboratory Parameter	SI Units	Conversion Factor ^a	Traditional Units	PCS Criteria ^b Low Values	PCS Criteria ^b High Values
Hematology	1	L		L	II.
Hemoglobin	g/L	0.1	g/dL	< 0.9 × LLN	_
Hematocrit	ratio	100	%	< 0.9 × LLN	_
White cell count	10 ⁹ /L	1	$10^3/\mu L$	≤ 2.5	≥ 15
Eosinophils absolute cell count	10 ⁹ /L	1	$10^3/\mu$ L	_	≥ 1.5
Neutrophils absolute cell count (not Black)	10 ⁹ /L	1	$10^3/\mu L$	< 1.5	> 15.0
Neutrophils absolute cell count (Black)	10 ⁹ /L	1	$10^3/\mu$ L	< 1.1	> 15.0
Lymphocyte absolute cell count	10 ⁹ /L	1	$10^3/\mu L$	< 0.75	≥ 5.0
Platelet count	10 ⁹ /L	1	$10^3/\mu L$	< 125.000	≥ 700
Chemistry	1		l .	l	I
Albumin	g/L	0.1	g/dL	< 27	
Alkaline phosphatase	U/L	1	U/L	_	≥ 2 × UNL
ALT	U/L	1	U/L	_	≥ 3 × UNL
AST	U/L	1	U/L		≥ 3 × UNL
Blood urea nitrogen	mmol/L	2.8011	mg/dL	_	> 1.3 × UNL
Calcium	mmol/L	4.008	mg/dL	< 1.97	> 2.77
Cholesterol	mmol/L	38.6698	mg/dL		> 7.75
Creatinine	μmol/L	0.0113	mg/dL	_	> 1.3 × UNL
Glucose, fasting	mmol/L	18.015	mg/dL	< 3.4	> 6.16
Potassium	mmol/L	1	mEq/L	< 3.4	> 5.3
Sodium	mmol/L	1	mEq/L	< 131	> 146
Total bilirubin	μmol/L	0.0585	mg/dL	_	> 2 × UNL
Urinalysis	•	-	·		·
Protein	_	_	_		≥ 2 +
Glucose	_				≥ 1 +

a Conversion factor is the multiplication factor to convert from SI units to traditional units.

b Criteria refer to SI units.

ALT = alanine aminotransferase; AST = aspartate aminotransferase; LLN = lower limit of normal of laboratory reference range; PCS = potentially clinically significant; SI = Le Système International d'Unités (International System of Units); UNL = upper normal limit of laboratory reference range.

Final Version

All laboratory abnormalities that occurred before dosing for a given treatment phase will be excluded from the tables but will be included in the listings. This includes any unscheduled laboratory assessments.

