3.2.5. Definitions and Terminology

Baseline Value

For quantitative safety measures, Baseline will be defined as the last valid evaluation completed before the study drug administration on Day 1. For ECG measures, including QTcF, Baseline will be defined as the mean of the triplicate set (total of 3 ECGs) performed pre-dose on Day 1 in Treatment Phase 1. This will also be referred to as Study Baseline.

A second Baseline will be used and will be referred to as the Treatment Phase 2 Baseline. For ECG, Treatment Phase 2 Baseline will be the mean of the triplicate ECGs (total of 3 ECGs) performed predose on Day 8.

Study Day

Study Day is defined relative to Day 1. Thus, the study day of an event occurring on or after Day 1 is calculated as:

Study Day = event date - date of Day 1 + 1.

The study day of an event occurring prior to Day 1 is calculated as:

Study Day = event date - date of Day 1.

Days on Study

Days on Study is calculated as Final Day on Study based on the EOS eCRF page – First Day on Study Drug + 1.

Treatment Phase Day

The study day within a treatment phase. Treatment Phase Day will be defined within each Treatment Phase 1 or 2.

Final Version

Treatment Phase Day = event date - date of Day 1 of Treatment Phase X + 1.

Study Time Point

Study Time Point is the nominal time point as recorded on the CRF.

Change from Baseline

Change from Baseline for a given endpoint is defined as the Study Time Point X value minus the Baseline Value. Change from Baseline may be study-specific (i.e., across all study phases), or Treatment Phase-specific (within any specific Treatment Phase). In the latter case, Baseline will be Treatment Phase specific.

Adverse Event

An adverse event is any untoward medical occurrence in a clinical study subject administered a medicinal (investigational or non-investigational) product. An adverse event does not necessarily have a causal relationship with the treatment. An adverse event can, therefore, be any unfavorable and unintended sign (including an abnormal finding), symptom, or disease temporally associated with the use of a medicinal (investigational or non-investigational) product, whether or not related to that medicinal (investigational or non-investigational) product.

This includes any occurrence that is new in onset or aggravated in severity or frequency from the Baseline condition, or abnormal results of diagnostic procedures, including laboratory test abnormalities.

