A Treatment-emergent Clinically Significant Laboratory Abnormality is defined as any post-Baseline laboratory assessment occurring from Day 1 to the EOS determined to be clinically significant by the investigator, and for which the Baseline is not considered clinically significant. If the Baseline value is missing, normal, or not clinically significant, any clinically significant abnormality that occurs following initiation of study drug is considered treatment-emergent.

Concomitant Medications

Concomitant medications are those medications taken on or after the initiation of roluperidone on Day 1 of Treatment Phase 1. This definition includes medications that started prior to the initiation of roluperidone and continued concomitantly with roluperidone.

Prior Medications

Prior medications are those medications taken and stopped prior to the initiation of roluperidone.

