14.2.1.3 Clinical Global Impression- Severity Rating (CGI-S) by Treatment Phase, Safety Set

Pharmacokinetics

14.2.3.1.1	Plasma Concentrations of Roluperidone, PK Set
14.2.3.1.2	Plasma Concentrations of Roluperidone Metabolite BFB-520, PK Set
14.2.3.1.3	Plasma Concentrations of Olanzapine, PK Set
14.2.3.2.1	Plasma PK Parameters for Roluperidone, PK Set
14.2.3.2.2	Plasma PK Parameters for Roluperidone Metabolite BFB-520, PK Set
14.2.3.2.3	Plasma PK Parameters for Olanzapine, PK Set
14.2.3.2.4	Plasma PK Parameters for Roluperidone, PK Completer Set
14.2.3.2.5	Plasma PK Parameters for Roluperidone Metabolite BFB-520, PK Completer Set
14.2.3.2.6	Plasma PK Parameters for Olanzapine, PK Completer Set
Safety	
14.3.1.1	Overall Summary of Treatment-Emergent Adverse Events, Safety Set
14.3.1.2	Treatment-Emergent Adverse Events by System Organ Classification and
	Preferred Term, Safety Set
14.3.1.3	Treatment-Emergent Adverse Events by System Organ Classification, Preferred
	Term, and Maximum Severity, Safety Set
14.3.1.4	Treatment-Emergent Adverse Events by System Organ Classification, Preferred
	Term, and Maximum Relationship, Safety Set
14.3.1.5	Treatment-Emergent Adverse Events Related to Study Drug by System Organ
	Classification, Preferred Term, and Maximum Severity, Safety Set
14.3.1.6	Treatment-Emergent Serious Adverse Events by System Organ Classification and
	Preferred Term, Safety Set
14.3.1.7	Treatment-Emergent Serious Adverse Events Related to Study Drug by System
	Organ Classification, Preferred Term, and Maximum Severity, Safety Set
14.3.1.8	Treatment-Emergent Adverse Events of Special Interest by System Organ
	Classification and Preferred Term, Safety Set

Minerva Neuroscien	ces, Inc.
MIN-101C18	

Statistical Analysis Plan Final Version

14.3.1.9	Treatment-Emergent Adverse Events Leading to Discontinuation of Study Drug by
	System Organ Classification and Preferred Term, Safety Set
14.3.1.10	Treatment-Emergent Adverse Events Leading to Death by System Organ
	Classification and Preferred Term, Safety Set
14.3.5.1	Clinical Laboratory Hematology Parameters by Time Point, Safety Set
14.3.5.2	Clinical Laboratory Chemistry Parameters by Time Point, Safety Set
14.3.5.3	Clinical Laboratory Urinalysis Parameters by Time Point, Safety Set
14.3.5.4	Potentially Clinically Significant Laboratory Values Occurring Post-Baseline,
	Safety Set
14.3.5.5	Clinical Laboratory Parameter Post-Baseline Shifts, Safety Set
14.3.6.1	Vital Signs by Time Point, Safety Set

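### The SAP gives two incompatible rules for treatment-emergent clinically significant laboratory abnormalities, so the same data can give different counts

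*SAP*

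**What the plan says.** **SAP Section 3.2.5 (definition).** A treatment-emergent clinically significant laboratory abnormality is a post-baseline result "determined to be clinically significant by the investigator, and for which the Baseline is not considered clinically significant". The next sentence repeats the baseline condition: "If the Baseline value is missing, normal, or not clinically significant, any clinically significant abnormality that occurs following initiation of study drug" counts as treatment-emergent.

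**SAP Section 5.3.2 (analysis).** The summary uses the defined term: "The number and percentage of subjects experiencing treatment-emergent clinically significant laboratory abnormalities will be summarized by treatment group". Two instructions follow directly: "See Table 2 for parameter specific criteria", and "All abnormalities that occur post-baseline, regardless of Baseline status will be included". Table 2 is a list of fixed PCS limits. A later sentence sets a timing rule: "All laboratory abnormalities that occurred before dosing for a given treatment phase will be excluded from the tables".

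**Baseline.** SAP Section 3.2.5 states: "For quantitative safety measures, Baseline will be defined as the last valid evaluation completed before the study drug administration on Day 1". It then introduces a second baseline for Treatment Phase 2 but spells out its derivation only for ECG. Section 5.3.2 nevertheless uses a Treatment Phase 2 baseline for laboratory changes.

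**Planned output.** SAP Section 9 lists one laboratory abnormality count, Table 14.3.5.4, titled "Potentially Clinically Significant Laboratory Values Occurring Post-Baseline". Table 14.3.5.5 is the shift table. No table is listed for the Section 3.2.5 definition.

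**The concern.** One named endpoint has two deciders (the investigator, or fixed limits) and opposite baseline rules (exclude, or include). Under Section 5.3.2, a subject who enters beyond a Table 2 limit and does not change is labelled treatment-emergent.

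Laboratory evaluations belong to the primary objective (SAP Section 2), and the study has no parallel control arm. Whether a value is new relative to baseline is therefore central to reading the table. If the SAP does not settle the rule, the choice passes to whoever programs the table, in an open-label study whose data can be seen.

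**Working it through.** The plan states no figure on this point, so there is none to reproduce. The check compares the two rules and then shows how far a count can move.

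**1. The rules applied to one parameter in one subject**

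| Case | Section 3.2.5 | Section 5.3.2 |
|---|---|---|
| Limit newly crossed after dosing; investigator judges it significant | counted | counted |
| Beyond limit at baseline and after dosing; investigator's view unchanged | not counted | counted |
| Limit newly crossed; investigator judges it not significant | not counted | counted |
| Within limit, but investigator judges the result significant and baseline not | counted | not counted |

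The rules agree in the first case and disagree in the other three. The baseline conflict can only raise the Section 5.3.2 count. The conflict over who decides can move it either way.

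**2. Does another passage reconcile them?** The timing rule in Section 5.3.2 removes results obtained before dosing in a phase. It does not remove a post-dose result from a subject who was already abnormal, so the second case remains.

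**3. Can a subject enter beyond a Table 2 limit?** Yes. Table 2 flags fasting glucose above 6.16 mmol/L and cholesterol above 7.75 mmol/L. Protocol Section 4.3 sets no numeric limit for either. Exclusion 16 removes clinically significant abnormalities only if they are unresolved and the investigator thinks they can interfere with participation. Exclusion 24 covers low potassium, calcium and magnesium.

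**4. Size per subject.** SAP Section 3.1 plans about 18 subjects dosed in Phase 1 and at least 12 completing Phase 2. One subject is 100/18 = 5.6 points, or 100/12 = 8.3 points.

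Let m be the number of subjects with a new abnormality and k the number abnormal at baseline and still abnormal after dosing. Assume the investigator and Table 2 agree. Section 3.2.5 then gives m/n and Section 5.3.2 gives (m + k)/n. With m = 2 and n = 18 (hypothetical):

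| k | Section 3.2.5 | Section 5.3.2 |
|---|---|---|
| 0 | 2/18 = 11.1% | 2/18 = 11.1% |
| 1 | 2/18 = 11.1% | 3/18 = 16.7% |
| 2 | 2/18 = 11.1% | 4/18 = 22.2% |
| 3 | 2/18 = 11.1% | 5/18 = 27.8% |

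**5. Chance that the baseline rules give different counts.** Let p be the share of subjects abnormal at baseline and still abnormal after dosing, independent between subjects. The chance that k is at least 1 is 1 − (1 − p)^n. The documents do not give p, so a range is shown:

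| p (assumed) | n = 18 | n = 12 |
|---|---|---|
| 5% | 60% | 46% |
| 10% | 85% | 72% |
| 20% | 98% | 93% |

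**6. The baseline in Phase 2.** The schedule (SAP Section 1.2) places chemistry and hematology at Screening, Day -1, Day 7, Day 17 and the end-of-study visit. Suppose an abnormality is new on Day 7 and still present on Day 17. Measured from the pre-Day 1 baseline, it is treatment-emergent under both treatment groups. Measured from the Day 7 draw, it is treatment-emergent under roluperidone alone only. The SAP does not say which baseline applies to this count.

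**The case against.** The strongest reply is that the intended output can be inferred. Table 14.3.5.4 is titled as a PCS count, SAP Section 5.3.4 uses the same sentence about baseline status for PCS vital signs, and Protocol Section 8.5 promises only PCS frequencies. On this reading, Section 5.3.2 used the wrong label and only one count was ever planned. That is probably the intent, and it makes the repair easy. It does not remove the conflict: Section 5.3.2 uses the defined term, which the vital signs text does not, and on this reading the Section 3.2.5 definition has no count table.

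Three stronger inferences are tempting, and the documents do not support them.

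- *The two counts must differ.* They coincide if no subject is abnormal at baseline and the investigator always agrees with Table 2. The eligibility criteria narrow the scope for baseline abnormality, though they do not close it.
- *Pre-existing abnormalities will be reported as drug effects.* The table is descriptive and does not itself assign cause. Changes from baseline, the shift table and the listings partly show baseline status. The protection is incomplete, because the shifts refer to the normal range and not to the Table 2 limits.
- *The comparison of roluperidone alone with the combination is diluted.* If the same n subjects contribute to both phases, (m2 + k)/n − (m1 + k)/n = (m2 − m1)/n, where m1 and m2 are the new cases in each phase. The difference is unchanged; only a ratio shrinks. If denominators differ, two unchanged subjects give 2/18 = 11.1% and 2/12 = 16.7%. That 5.6-point gap comes from the denominators and is not dilution. Twelve is also a minimum number of completers, and safety is analysed by treatment received (SAP Section 4.2), so the Phase 2 denominator may be larger.

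**Conclusion.** The contradiction is real and lies within the current SAP. Sections 3.2.5 and 5.3.2 differ on both the decider and the baseline condition, and no text ranks one above the other. As Section 5.3.2 stands, an unchanged abnormality present at baseline can be labelled treatment-emergent in a summary that serves the primary objective.

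The per-subject size is exact arithmetic at the assumed denominators. How many subjects are affected is unknown, and the percentages and chances above rest on assumed values of m, k and p. The consequence is an ambiguous descriptive safety table. It should be corrected, but it leaves the sample size, the error rates and the pharmacokinetic estimates untouched.

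**What to change.** Amend the SAP before database lock:

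1. In Section 5.3.2, rename the existing count (Table 14.3.5.4) as post-baseline PCS values per Table 2, whatever the baseline status. Keep the sentence on baseline status for this output only, and remove the term *treatment-emergent* from it.
2. Add a separate column or table for treatment-emergent abnormalities: Table 2 limit met post-baseline and not met at the applicable baseline. Either rewrite the Section 3.2.5 definition to match, or keep its investigator-judged definition and give it its own output.
3. State the laboratory baseline for Treatment Phase 2, and say which baseline applies to each phase in these counts. One option is the last valid value before Day 8 dosing, which on the schedule is the Day 7 draw. That draw would then be both a Phase 1 outcome and the Phase 2 baseline, and the SAP should say so.

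The cost is SAP wording and one additional column or table. No new data collection is needed.
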